## STUDY 2:

Change over time of:

## Primary endpoint

o M-mode method of diaphragm movement (ultrasound, only on the right hemidiaphragm).

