## STUDY 2:

The etiology of shortness of breath is multifactorial, and shortness of breath can be a symptom of a wide range of lung or heart diseases. In failing heart pump function, shortness of breath is one of the most frequent symptoms. Heart failure can be treated with various types of medicine, but in severe heart failure so that sufficient circulation cannot be maintained, heart transplantation may be the only treatment. Shortage of transplant organs results in waiting time for transplantation. Therefore, an LVAD has been developed that can maintain adequate blood circulation as either temporary treatment before heart transplantation or as definitive treatment in patients who cannot undergo regular heart transplantation. The LVAD is implanted in the thorax and helps pump blood from the left ventricle into the aorta. The LVAD is located on top of the left hemidiaphragm and can therefore inhibit the movement of the diaphragm. Thereby, the LVAD can give rise to shortness of breath, and in patients who have concurrent heart failure, it can thus be difficult to assess whether shortness of breath is due to heart failure or reduced diaphragm function. Treatment that these conditions are different.

Heart transplantation entails a complete replacement of the heart. Due to the close relationship with the phrenic nerve, this can be damaged during the operation and thus result in reduced diaphragm function.

Some diseases, e.g. Cancer of the lung, mediastinum and esophagus requires thoracic surgery. Nerves to the diaphragm can be damaged during the operation and thereby cause reduced diaphragm function, which can lead to shortness of breath. Pleural effusion is common after thoracic surgery and also manifests as shortness of breath. In addition, patients often have other competing diseases such as chronic obstructive pulmonary

disease (COPD) or heart failure, which can also cause shortness of breath. This results in complex diagnostic conditions and complicates the investigation of shortness of breath after thoracic surgery.

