## HYPOTHESIS/AIM

- 1. To compare the precision of different ultrasound examination methods for assessing diaphragm function compared with X-ray translucency.
- 2. Investigate whether LVAD implantation, heart transplantation and thoracic surgery affect diaphragm function.

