## STUDY 2:

Inclusion criteria:

- o Completed informed consent.
- One of the following:
  - Planned LVAD implantation / Heart transplant
  - Planned surgery for lung cancer/esophageal cancer. For lung cancer, the planned operation must be the removal of one or more lung lobes.

Exclusion criteria:

- Known diaphragm dysfunction
- o Neuromuscular disease
- Pleural effusion (over 1 cm)
- Pneumothorax

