## ULTRASOUND EXAMINATIONS:

The participants are examined in a standing/sitting position with ultrasound in the mid-axillary line with the liver/spleen as a reference point on the right and left side. A movie clip is saved for later analysis.

Diaphragm movement is measured in 3 different ways: M-mode, Area method and B-mode. [1] [2] [3] [4] Diaphragm thickening fraction is measured in 1 way. [5]

Normal and deep breathing is carried out.

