#### Secondary endpoints

- Area method for diaphragm movement (ultrasound and transillumination for LVAD patients).
- B-mode method of diaphragm movement (ultrasound).
- Lung function (FEV1, FVC, FRC).

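### Study 2's primary endpoint reads only the right hemidiaphragm, so a null primary result in LVAD patients could not rule out an effect lying mainly on the left, where the plan places the device

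*Combined protocol and SAP*

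**What the plan says.** - **Aim** (Hypothesis/aim, item 2): "Investigate whether LVAD implantation, heart transplantation and thoracic surgery affect diaphragm function".
- **LVAD mechanism** (Background, Study 2): "The LVAD is located on top of the left hemidiaphragm and can therefore inhibit the movement of the diaphragm". This is the only mechanism in that section tied to a named side. Whether the right side is also affected is not stated.
- **Primary endpoint** (Endpoints, Study 2): change over time of "M-mode method of diaphragm movement (ultrasound, only on the right hemidiaphragm". It is the same for all groups, and no section explains the choice of side.
- **Secondary endpoints** (Endpoints, Study 2): "Area method for diaphragm movement (ultrasound and transillumination for LVAD patients" and "B-mode method of diaphragm movement (ultrasound", plus FEV1, FVC and FRC. No side is named for the two movement measures.
- **Acquisition** (Ultrasound examinations): participants are scanned with "the liver/spleen as a reference point on the right and left side", and a clip is stored for later reading. The section does not say whether M-mode is recorded on the left.
- **Analysis** (Data analysis, Study 2): a before/after repeated-measures analysis with participants as their own controls. It has no term or separate analysis for side or for LVAD patients.
- **Transillumination**: the area endpoint lists it for LVAD patients, whereas the transillumination section under Surveys confines it to Study 1, and the Study 2 examination schedule allows only lung function testing and ultrasound.

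**The concern.** The plan gives a left-sided mechanism for the LVAD, makes the LVAD effect an aim, and then bases the primary endpoint on the other side alone. Followed exactly, the primary reads the side opposite the stated mechanism in every LVAD patient.

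What is at stake is how a null primary result would be read. If LVAD patients show no change on the right, the natural conclusion is that the device leaves the diaphragm unaffected. That does not follow if the effect lies mainly on the left. Without a committed left-side analysis, any later left-side result would also be open to the charge that the side was chosen after the data were seen.

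**Working it through.** The point rests on the text. The arithmetic only confirms the plan's own figure and shows how the assumptions behave.

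**1. The plan's own sample size.** Strength calculation, Study 2 (lung/oesophageal patients) gives a mean of 6.65 mm, SD 2.38 mm, a 20% change, power 0.9, alpha 0.05 and 36 patients.
- Change to detect: 0.20 × 6.65 = 1.33 mm. Standardised: 1.33 / 2.38 = 0.559, taking 2.38 as the SD of the change.
- Normal approximation: ((1.960 + 1.282) / 0.559)² = 33.6, so 34.
- Paired t-test (noncentral t, two-sided): n = 36, power 0.903.

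The 36 reproduces, so the sample-size arithmetic is not the problem. The side to which 6.65 and 2.38 refer is not stated. The LVAD/transplant group has no power calculation, only an expected intake of about 40 over two years with no split.

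**2. Could another part of the plan supply the left-side answer?**
- Area and B-mode endpoints: not limited to the right, so they could, but no side is named.
- Lung function: not side-specific.
- Transillumination in LVAD patients: listed in one place and excluded in two others, so it cannot be relied on as it stands.
- Data analysis, Study 2: nothing specific to side or to LVAD.

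A left-side analysis is therefore possible but not committed.

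**3. Illustration: how the right-side test behaves.** Assumptions not in the documents: left-side fall of 20% (1.33 mm), SD of change 2.38 mm, and a right-side change equal to a fraction r of the left. The noncentrality is r × 0.559 × √n. The figure of 40 is an upper limit (every patient an LVAD patient); 20 is an assumed split.

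| r | power, n = 20 | power, n = 40 |
|---|---|---|
| 0 | 0.05 | 0.05 |
| 0.1 | 0.06 | 0.06 |
| 0.25 | 0.09 | 0.14 |
| 0.5 | 0.22 | 0.41 |
| 1 | 0.66 | 0.93 |

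At r = 0 the test rejects only at the alpha rate, whatever the sample size. At r = 1 nothing is lost by reading the right. The documents give no value for r.

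**4. Precision of a left-side LVAD estimate.** The half-width of the 95% confidence interval is t(0.975, n−1) × SD / √n. LVAD numbers and the SD range are assumed; no left-side SD is given.

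| LVAD patients | SD 2.38 mm | SD 1.8 to 3.0 mm |
|---|---|---|
| 10 | 2.262 × 2.38 / 3.162 = 1.70 mm | 1.29 to 2.15 mm |
| 20 | 2.093 × 2.38 / 4.472 = 1.11 mm | 0.84 to 1.40 mm |
| 30 | 2.045 × 2.38 / 5.477 = 0.89 mm | 0.67 to 1.12 mm |

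Against 6.65 mm, the middle column is 26%, 17% and 13%. That is enough for an estimate with its interval, but not for a power claim.

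**The case against.** **The right side was chosen for continuity.** Study 1's movement endpoints are all right-sided, and no ultrasound method is regarded as sufficiently validated (Background, Study 1). Comparing the same measure across both studies is a fair reason to keep right-side M-mode as primary. This stands, but the plan does not state it, and it does not answer the LVAD question.

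**The secondary endpoints already cover the left.** The restriction to the right is explicit for the primary and absent from the area and B-mode endpoints, although Study 1's versions carry it, and both sides are scanned. On a natural reading the secondaries are bilateral. This has force: the left side is not ruled out. But a reading that has to be inferred is not a pre-specified analysis.

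**The right side may change too.** It may, and the primary would then detect it, subject to its size. The point is confined to null primary results.

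**Does the mismatch extend to other operations?** A reader might infer that it covers left-sided lung resections, since eligibility sets no side ("For lung cancer, the planned operation must be the removal of one or more lung lobes"). The documents do not support this: for thoracic surgery the background says only "Nerves to the diaphragm can be damaged during the operation and thereby cause reduced diaphragm function", with no statement that the effect is one-sided. Nor does it give a side for heart transplantation or oesophageal surgery.

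**Conclusion.** The concern holds for LVAD patients and for the primary endpoint. If the LVAD effect lies mainly on the left, a null right-side primary result in these patients cannot separate no effect from measurement of the other side, and no pre-specified analysis would settle it. The condition matters, because the documents do not say how far the right side is affected.

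It applies to every LVAD patient, but their number within the expected 40 or so is not given, and no loss can be computed from the documents alone. A reader might infer from the illustration that Study 2 is underpowered. That does not follow: the planned 36 reproduces, its 20% is a change in the endpoint actually measured, and the LVAD/transplant cohort is pragmatic with no power claim. Nor does it follow that Study 2 as a whole cannot address the LVAD mechanism, because left-side secondary readings remain open. The gap touches a named aim and is worth fixing.

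**What to change.** 1. Keep right-side M-mode as the primary and state the reason in the endpoint section, for example continuity with Study 1.
2. State the side(s) for the area and B-mode secondary endpoints.
3. Pre-specify as a secondary endpoint the before-after change in left-hemidiaphragm movement in LVAD patients, over the visits already scheduled for them (day before surgery, 14 days, 3 months), reported separately from transplant patients. Show the right-side change by the same method alongside. Give each as an estimate with a 95% confidence interval and no power claim. Do not use a side-to-side difference as the test, because a bilateral effect would cancel out of it.
4. State that a null right-side primary result in LVAD patients does not by itself show absence of a diaphragm effect.
5. Reconcile the secondary endpoint list with the transillumination section and the Study 2 examination schedule on transillumination in LVAD patients.

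**Cost.** Mainly wording, one added analysis and the reading of left-side clips that the ultrasound section indicates are already stored. It must be confirmed that M-mode is recorded on the left; otherwise the area or B-mode method would be used on both sides. Left-side views may be missing and should be counted and reported. Study 1 plans no left-side ultrasound comparison, which is why the left side is proposed as secondary. The primary test and the planned sample size do not change.

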#### Secondary endpoints

- Area method for diaphragm movement (ultrasound and transillumination for LVAD patients).
- B-mode method of diaphragm movement (ultrasound).
- Lung function (FEV1, FVC, FRC).

## STRENGTH CALCULATION

## STUDY 1:

There is no data available for test-retest variance within ultrasound methods or fluoroscopy. It is therefore not possible to make a power calculation of how the spread in the comparison of two methods will be (Limits of agreement with Bland-Altman analysis). The starting point is therefore the bias (absolute difference in mean value) between an ultrasound method (m-mode method) and transillumination. As this is a methodological study, greater requirements are set than in study 2 (see below) for which bias can be detected. Assuming equal variation for the two methods, a detection of bias of 10% (SD 36%, own data for M-mode method) will require 92 participants (power 0.8 and alpha 0.05). Due to uncertainty about SD on the screening method, it is desired to include 100 participants.

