## ETHICAL CONSIDERATIONS

## STUDY 1:

Ultrasound examinations and lung function examination are without any kind of risks or discomfort for the participants and the examinations do not contain any ethical considerations.

The participants will be X-rayed. The radiation dose is minimal and the expected, accumulated dose of 0.1-1mSievert must be compared to being exposed to approx. 3 mSv for background radiation annually. The expected radiation dose corresponds to an increased risk of serious cancer of 1 in 100,000. If it turns out that there is good correlation and agreement between ultrasound methods and fluoroscopy, there will be no need for fluoroscopy in the future if dysfunction of the diaphragm muscle is suspected, and future patients will therefore be spared radiation. [6] It will also be possible to reduce the radiation dose employees are exposed to. In study 1, only subjects aged  $\geq$ 50 years are included in order to minimize the risk of developing cancer secondary to the experiment. There have been no studies in which the radiation dose during fluoroscopy is indicated, as it depends on the apparatus and method. In this study, we record the total radiation dose, and the total radiation dose is closely monitored.

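### Study 1 sets aside limits of agreement for a reason that does not hold, is sized on mean bias instead, and fixes no acceptable limit for its agreement conclusion

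*Combined protocol and SAP*

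**What the plan says.** The Study 1 part of the strength calculation opens with the statement "There is no data available for test-retest variance within ultrasound methods or fluoroscopy". From this it concludes, naming Bland-Altman limits of agreement, "It is therefore not possible to make a power calculation of how the spread in the comparison of two methods will be". It continues: "The starting point is therefore the bias (absolute difference in mean value) between an ultrasound method (m-mode method) and transillumination". The calculation that follows reads "Assuming equal variation for the two methods", then "a detection of bias of 10% (SD 36%, own data for M-mode method) will require 92 participants", at "power 0.8 and alpha 0.05". The target is then rounded up: "Due to uncertainty about SD on the screening method, it is desired to include 100 participants".

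The Study 1 endpoints section plans correlations and Bland-Altman analysis where relevant. The Study 1 data analysis section compares each method with fluoroscopy by a paired t-test (Wilcoxon as the alternative), with a null hypothesis of no difference, and adds a Bland-Altman plot and a correlation. The ethics section for Study 1 makes the end of fluoroscopy conditional: "If it turns out that there is good correlation and agreement between ultrasound methods and fluoroscopy". No section says how narrow the limits must be for agreement to count as good.

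**The concern.** The width of the limits of agreement is governed by the SD of the between-method differences within a person. Test-retest variance contributes to that SD but is not needed to say how precisely a given n will estimate the limits. The word 'therefore' in the protocol shows that the choice of mean bias followed from the claimed impossibility.

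Mean bias answers a different question. Two methods can agree on average and still differ widely in individual people. A non-significant paired test does not demonstrate agreement, and a significant but small bias does not refute it. With no limit fixed in advance, whether the observed agreement is good enough to drop fluoroscopy would be decided after the data are seen.

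**Working it through.** **Inputs.** From the Study 1 strength calculation: bias 10%, SD 36% (M-mode, own data), equal variation for both methods, power 0.8, alpha 0.05, 92 required and 100 planned. The between-method correlation r and the acceptable limit are not given; r is an assumption below.

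**The plan's own figure.** For a two-sided paired comparison, n = (SD × (1.960 + 0.842)/10)². With SD = 36 this is 101.7, so 102 (104 with the t distribution), not 92. That mismatch is a separate matter and carries no weight here. What matters is that the formula needs the SD of paired differences, SD_d. The 36% matches the between-person SD in the Study 2 calculation (2.38/6.65 = 35.8%). Using it as SD_d with equal variation amounts to assuming r = 0.5, since SD_d = 36 × √(2(1 − r)) = 36 when r = 0.5.

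**Precision of a limit, needing only n.** SE(limit) = SD_d × √(1/n + 1.96²/(2(n − 1))).

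- n = 100: √(0.0100 + 3.8416/198) = 0.171; 95% CI half-width 1.96 × 0.171 = 0.336 SD_d.
- n = 92: half-width 0.350 SD_d.

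No test-retest figure enters.

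**Absolute width, needing an assumed r** (36% per method, n = 100):

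| Assumed r | SD_d | Limits: bias ± 1.96 SD_d | 95% CI half-width of each limit |
|---|---|---|---|
| 0 | 50.9% | ±99.8% | 17.1 points |
| 0.5 | 36.0% | ±70.6% | 12.1 points |
| 0.8 | 22.8% | ±44.6% | 7.7 points |
| 0.9 | 16.1% | ±31.6% | 5.4 points |
| 0.95 | 11.4% | ±22.3% | 3.8 points |

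**Bias against spread.** With SD_d = 36% and n = 100, the mean bias is known to ±1.984 × 36/√100 = ±7.1 points, while the limits are still about ±71%. A reassuring bias result can therefore coexist with very poor individual agreement.

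**Power for an agreement rule.** If both outer 95% bounds must lie inside a margin, and true bias is zero, a noncentral-t approximation gives 80% power at n = 162, 108, 78 and 31 for margins of 2.4, 2.5, 2.6 and 3.0 SD_d. At n = 100, 80% power needs a margin of about 2.52 SD_d. These margins are illustrative, as the documents give none.

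**The case against.** The best defence is that the protocol speaks only of a power calculation for how large the spread will be. Absolute spread does depend on an SD of differences that the documents do not give, and formal power also needs a margin. The width of the table above, from ±22% to ±100%, supports that. This part stands: a reader might infer that the protocol says nothing at all can be calculated, and it does not say that. But the defence does not rescue the reasoning, because the bias calculation adopted instead needs the same missing SD.

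It is also fair that Bland-Altman analysis and correlation are already planned, so limits will be estimated, and that the replacement statement sits in the ethics section and asks for correlation and agreement, not for absence of bias. This stands too. The gap is that the formal test does not address agreement and that good agreement is undefined.

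Three stronger readings are tempting and are not supported:

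- **That 100 participants are too few.** A half-width of 0.34 SD_d is a usable precision. Adequacy cannot be judged without a margin.
- **That precision within each third of the sample is inadequate.** At n = 33 the half-width would be about 0.59 SD_d, but the 34/33/33 split is a recruitment target and no group-specific agreement analysis is planned.
- **That the 20% in the Study 2 calculation is the plan's own agreement limit.** It is a before-after change in surgical patients, used to size a test of mean change, and the protocol says Study 1 is held to greater requirements. Borrowing it would demand r of about 0.960 for the limits to reach ±20% with zero bias, or about 0.971 for the expected outer bounds. Even at r = 0.971 and n = 100, the outer-bound rule would be met only about 36% of the time with zero bias, and about 0.1% with a 5% bias.

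**Conclusion.** The concern holds in a limited form. The stated reason for setting limits of agreement aside is unsound: their precision in SD_d units follows from n alone (0.34 SD_d at n = 100), and the bias calculation needs SD_d anyway. The formal test of zero mean difference cannot support a conclusion of agreement, and no acceptable limit is pre-specified.

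The absolute figures (±71%, ±45% and ±32% at r = 0.5, 0.8 and 0.9) rest on 36% per method, equal variation, approximately normal differences and an assumed r. They show how much the answer depends on r; they do not predict the result. The documents do not support saying that agreement goes unanalysed or that the sample size must change. The point should be corrected before the data are seen.

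**What to change.** Keep n = 100 and make three changes.

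1. In the Study 1 strength calculation, replace the sentence on impossibility and the 'therefore' that follows with a statement such as: *100 participants estimate each limit of agreement to within about 0.34 SD of the paired differences.* Add absolute values over a stated range of r, as in the table above.
2. In the Study 1 endpoints and data analysis sections, pre-specify the largest acceptable between-method difference, justified by the sponsor for Study 1 and not borrowed from the Study 2 figure. Conclude agreement for the primary M-mode comparison only if the outer 95% confidence bounds of both limits lie inside it. Report the paired t-test as an estimate of bias only.
3. State the chance of meeting that rule at n = 100 over plausible values of r and of bias. Bias matters: the 80% figure at a margin of about 2.52 SD_d assumes none.

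The cost is protocol wording and a short calculation, with no added participants or radiation. The real downside is that the sponsor commits in advance to a limit that may prove hard to meet.

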## STUDY 2:

## LUNG/OESOPHAGEAL CANCER PATIENTS:

Data from own research shows diaphragm movement of 6.65mm (SD 2.38) (M-mode method). At a power of 0.9 and alpha 0.05, 36 patients are needed (before-after situation) to show a 20% change that is considered clinically relevant. In order to compensate for drop-outs and an unknown diaphragm movement in particular lung surgery patients, it is desired to include 50 patients.

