## SUMMARY OF DESIRED NUMBER OF INCLUDED PATIENTS

## STUDY 1:

We want 100 patients (34 healthy, 33 pulmonary medicine patients and 33 patients who have had a heart transplant/LVAD) included, distributed equally between the 3 groups to compensate for drop-outs and increase power.

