## DATA ANALYSIS

#### STUDY 1:

Movement is measured continuously (centimeters or square centimeters) and calculated as a mean with standard deviation for the various ultrasound measurements. Correlation between diaphragm movement and sex, age, BMI is analyzed with multivariable analysis of variance, MANOVA.

The different measurement methods are compared individually with the golden standard with the paired T-test (Wilcocon's test if non-parametric). The 0 hypothesis is that there is no difference between the index method and the golden standard. Data is also depicted with a Bland-Altman plot and correlation between the index test and the golden standard.

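### Study 1's 92 participants do not follow from the stated inputs: 104 are needed if 36% is the SD of paired differences, and otherwise a between-method correlation is missing

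*Combined protocol and SAP*

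**What the plan says.** The Study 1 part of the Strength calculation section explains that "There is no data available for test-retest variance within ultrasound methods or fluoroscopy", so the limits of agreement cannot be powered. It falls back on the mean bias: "The starting point is therefore the bias (absolute difference in mean value) between an ultrasound method (m-mode method) and transillumination". It assumes that the two methods vary equally and concludes that "a detection of bias of 10% (SD 36%, own data for M-mode method) will require 92 participants (power 0.8 and alpha 0.05"). The target is then rounded up: "Due to uncertainty about SD on the screening method, it is desired to include 100 participants". The summary of desired numbers gives the 100 two further purposes: "distributed equally between the 3 groups to compensate for drop-outs and increase power".

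The Study 1 part of the Data analysis section fixes the test. Each ultrasound method is "compared individually with the golden standard with the paired T-test", with a null hypothesis of no difference. That null implies a two-sided test, although sidedness is not stated.

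The Study 2 calculation, directly below, starts from the group's own M-mode data (mean 6.65 mm, SD 2.38): "At a power of 0.9 and alpha 0.05, 36 patients are needed (before-after situation) to show a 20% change".

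**The concern.** A paired t-test for bias is powered on the SD of the paired differences. The section gives one SD, 36%, attributed to the group's own M-mode data, and does not say what it is the SD of. There are two natural readings:

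- **Reading A:** 36% was entered as the SD of the differences.
- **Reading B:** 36% is the between-person SD of each method, as the equal-variation assumption suggests. The SD of differences then also needs the correlation between M-mode and fluoroscopy, which appears nowhere.

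The stated 92 does not come out under reading A and cannot be computed under reading B. This is the sample size for Study 1's primary endpoint. The step from 92 to 100 is presented as protection against a wrong SD, and elsewhere against drop-out, so an error in the 92 removes or obscures that protection.

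**Working it through.** **Inputs.** Bias 10%, SD 36%, power 0.8 and alpha 0.05 (Strength calculation, Study 1); paired t-test with a null of no difference, taken as two-sided (Data analysis, Study 1); mean 6.65 mm, SD 2.38, 20% change, power 0.9 and n = 36 (Strength calculation, Study 2).

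**Formulas.** Normal approximation: n = ((z for alpha/2 + z for power) × SD of differences / bias)². Exact: the smallest n at which the noncentral t distribution (n − 1 degrees of freedom, noncentrality √n × bias / SD of differences) gives the required power.

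**Step 1: try to reproduce 92.**

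| Interpretation | n |
|---|---|
| Two-sided, SD of differences 36%, normal approximation: ((1.96 + 0.8416) × 3.6)² = 101.7 | 102 |
| Same, exact t | 104 |
| Same, SD unrounded at 2.38/6.65 = 35.8%, exact t | 103 |
| One-sided, exact t | 82 |
| Unpaired, SD 36% in each group | 204 to 205 per group |
| Log scale, difference ln 0.9, SD 0.36, normal approximation: 91.6 | 92 |
| Log scale, same inputs, exact t | 94 |

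Only the log-scale normal approximation reaches 92. The documents mention no log scale, and the section defines the bias as an absolute difference in means.

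**Step 2: check the method on Study 2.** A 20% change is 0.20 × 6.65 = 1.33 mm. With 2.38 used directly as the SD of differences, the exact two-sided paired t-test has power 0.903 at n = 36 and 0.895 at n = 35. This gives the stated 36 exactly (the normal approximation gives 33.6). Since 2.38/6.65 = 35.8%, Study 1's 36% appears to come from the same data. The method that reproduces Study 2 therefore gives 103 to 104 for Study 1.

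**Step 3: reading A, SD of differences 36%.**

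| n | Power for a 10% bias |
|---|---|
| 92 | 0.751 |
| 95 | 0.764 |
| 100 | 0.785 |
| 104 | 0.801 |

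The bias detectable with power 0.80 is 10.6% at n = 92 and 10.2% at n = 100. The row for 95 illustrates a loss of five participants; the protocol states no drop-out rate.

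**Step 4: reading B, each method's SD 36%.** The SD of differences is 36 × √(2(1 − r)). The values of r are assumptions, because the documents give none.

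| r | SD of differences (%) | n for power 0.80 | Power at n = 100 |
|---|---|---|---|
| 0.3 | 42.6 | 145 | 0.64 |
| 0.4 | 39.4 | 124 | 0.71 |
| 0.5 | 36.0 | 104 | 0.785 |
| 0.6 | 32.2 | 84 | 0.87 |
| 0.7 | 27.9 | 63 | 0.94 |
| 0.9 | 16.1 | 23 | >0.99 |

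Solving backwards, 92 gives power 0.80 when the SD of differences is 33.9%, that is r = 1 − 33.9²/(2 × 36²) ≈ 0.56.

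**Step 5: how much SD uncertainty the extra eight cover.** The largest SD of differences that keeps power at 0.80 is 33.9% at n = 92 and 35.3% at n = 100. Even if 92 were right, moving to 100 would absorb an SD only about 4.3% larger.

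**The case against.** The strongest counter-argument is that 92 may not be an arithmetic slip. Bias and SD are both given as percentages, which suits a relative scale, and a log-scale calculation gives 91.6, or 94 by exact t. The document reads as an imperfect translation, so much weight on its phrase for an absolute difference may be unfair. This explains where 92 may have come from. It does not make the figure right for the plan as written, which tests differences in centimetres with a paired t-test and mentions no transformation.

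Second, the wording favours reading B, under which 92 reflects an undisclosed correlation and not a wrong sum. The exact match with Study 2 supports reading A but does not prove it. This stands, and it is why 104 is offered only as a conditional figure.

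Third, the effect is small. The target is 100, which gives 0.785 under reading A and is enough under reading B once r reaches about 0.52. The two methods are recorded simultaneously in the same person, so low correlations may be unlikely. This also stands as a limit on the size of the problem, although no correlation is documented. The protocol also never says how much SD uncertainty the extra eight were meant to cover, so the 4.3% describes the margin and does not show a missed target.

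**Conclusion.** The concern holds. With the stated bias, SD, power and alpha, the planned paired t-test (taken as two-sided) does not give 92. If 36% is the SD of paired differences, 104 are needed, the planned 100 fall just short of the stated power, and no reserve is left for SD uncertainty or drop-out. If 36% is each method's own SD, 92 rests on an unstated correlation, and 100 may be too few or more than enough. This does not show Study 1 to be badly underpowered. The defect is that the stated power and the claimed margin are unsupported as written. It should be corrected.

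**What to change.** Rewrite the Study 1 paragraph of the Strength calculation section.

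1. State the SD of the paired differences (M-mode minus fluoroscopy), or the assumed between-method correlation, and say that the test is two-sided.
2. If 36% is the SD of differences, write: *With an SD of paired differences of 36%, a two-sided paired t-test at alpha 0.05 needs 104 participants for power 0.80 to detect a 10% bias; the planned 100 give power 0.79, or 0.80 for a bias of 10.2%.*
3. If 36% is each method's own SD, give the correlation used and its source, and show the sensitivity: 145 participants at r = 0.3, 104 at 0.5, 63 at 0.7 and 23 at 0.9.
4. Replace the statement that 100 allows for SD uncertainty with: *100 participants give power 0.80 if the SD of differences is at most 35.3%*, unless a smaller SD of differences can be justified.
5. If a log scale was in fact used, say so and bring the definition of bias and the planned test into line with it.

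Items 1 to 4 change wording only, with no added enrolment. The price is a stated power of 0.79 at 100 under reading A, or a correlation to disclose and defend under reading B. Item 5, if it applies, would also change the analysis scale.
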